Pancreatic	If amylase and/or lipase \geq CTCAE grade 3 has been demonstrated, these parameters must be assessed once at 2-4 days and once again at 7 days (± 1 day) and be repeated twice a week until resolution to \leq CTCAE grade 2 and then at least weekly until stabilization. A CT scan or other imaging study to assess the pancreas, liver and gallbladder must be performed within 1 week of the first occurrence of any \geq CTCAE grade 3 of amylase and/or lipase. In patients with serum triglycerides ≥ 500 mg/dL, urine amylase needs to be tested.
Endocrine/metabolic	For details on hyperglycemia management, please refer to Appendix 4: 'Fasting blood glucose management' .
Cardiac	For details on the follow-up and treatment of QT prolongation, please refer to Appendix 3 'Recommended follow up in case of QT-related findings during routine ECG'
Non-laboratory	Patients who experience non-laboratory AEs must be evaluated at least once a week following demonstration of the toxicity until resolution of the toxicity until stabilization of the toxicity, or until study completion.

Table 14-7 Dose reduction steps for pasireotide LAR monthly dosing q28d

Dose reduction*			
	Dose level - 0	Dose level - 1	Study Phase
Pasireotide LAR	60 mg q28d	40 mg q28d	Extension phase
Pasireotide LAR	40 mg q28d	30 mg q28d	Extension phase
Pasireotide LAR	30 mg q28d	20 mg q28d	Extension phase
Pasireotide LAR	20 mg q28d	10 mg q28d ***	LAR or Extension phases

*Dose reduction should be based on the worst toxicity demonstrated at the last dose.
*** The lowest dose allowed 10 mg.

Table 14-8 Dose modification for AEs, excluding LFT increase, QT prolongation and hyperglycemia

Adverse event	Action
CTCAE grade \leq 2	No drug adjustments
CTCAE grade \geq 3 and assessed as study drug related	
Reduce pasireotide to the next lower dose level.
 
• If the AE improves to grade \leq 2 before the next administration, increase dose back to the prior dose.• If the dose is increased and the AE recurs at a grade \geq 3, the dose should be reduced again. The patient should stay on this lower dose and no further dose titrations are allowed.• If the AE does not improve to grade \leq 2, the dose is to be reduced further. If the AE does not improve to grade \leq 2 on the minimum study dose, the treatment should be stopped.

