14.10.2 Treatment interruption and treatment discontinuation

All dose modifications should be based on the worst preceding toxicity.

Each patient is only allowed one dose reduction. In addition, a patient must discontinue treatment with pasireotide LAR if, after treatment is resumed at a lower dose, the toxicity recurs with the same or worse severity

Table 14-12 Criteria for interruption and re-initiation of pasireotide LAR

Recommended dose modifications for pasireotide LAR	
Worst toxicity CTCAE Grade* (value)	Recommended dose modification any time during a cycle of therapy
No toxicity	Maintain dose level
Hematologic	
Neutropenia (ANC)	
Grade 1 (ANC < LLN - 1500/mm ³)	Maintain dose level
Grade 2 (ANC < 1500 - 1000/mm ³)	Maintain dose level
Grade 3 (ANC < 1000 - 500/mm ³)	Omit dose until resolved to ≤ Grade 2, then - If resolved ≤ 7 days, then maintain dose level - If resolved > 7 days, then ↓ 1 dose level

Recommended dose modifications for pasireotide LAR	
Worst toxicity CTCAE Grade* (value)	Recommended dose modification any time during a cycle of therapy
Grade 4 (ANC < 500/mm ³)	Omit dose until resolved to ≤ Grade 2, then - If resolved ≤ 7 days, then maintain dose level - If resolved > 7 days, then ↓ 1 dose level
Thrombocytopenia	
Grade 1 (PLT < LLN - 75,000/mm ³)	Maintain dose level
Grade 2 (PLT < 75,000 - 50,000/mm ³)	Maintain dose level
Grade 3 (PLT < 50,000 - 25,000/mm ³)	Omit dose until resolved to ≤ Grade 1, then - If resolved ≤ 7 days, then maintain dose level - If resolved > 7 days, then ↓ 1 dose level
Grade 4 (PLT < 25,000/mm ³)	Omit dose until resolved to ≤ Grade 1, then ↓ 1 dose level
Febrile neutropenia (ANC < 1.0 x 10 ⁹ /L, fever ≥ 38.5°C)	Omit dose until resolved, then ↓ 1 dose level
Renal	
Serum creatinine	
< 2 x ULN	Maintain dose level
2-3 x ULN	Omit dose until resolved to ≤ Grade 1, then - If resolved ≤ 7 days, then maintain dose level - If resolved > 7 days, then ↓ 1 dose level
Grade 3 (> 3.0 - 6.0 x ULN)	Omit dose and discontinue patient from study treatment
Grade 4 (> 6.0 x ULN)	Omit dose and discontinue patient from study treatment
Hepatic	
Bilirubin	
< 2 x ULN	Maintain dose level
2-3 x ULN	Omit dose until resolved to ≤ Grade 1, then - If resolved ≤ 7 days, then maintain dose level - If resolved > 7 days, then ↓ 1 dose level
Grade 3 (> 3.0 - 10.0 x ULN)	Omit dose until resolved to ≤ Grade 1, then - If resolved ≤ 7 days, then maintain dose level - If resolved > 7 days, then ↓ 1 dose level

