Grade 4 (> 10.0 x ULN)	Omit dose and discontinue patient from study treatment NOTE: If grade 3 or 4 hyperbilirubinemia is due to the indirect (unconjugated) component only, and hemolysis as the etiology has been ruled out as per institutional guidelines (e.g. review of peripheral blood smear and haptoglobin determination), then ↓ 1 dose level and continue treatment at the discretion of the investigator
AST or ALT	
Grade 1 (> ULN - 2.5 x ULN)	Maintain dose level
Grade 2 (> 2.5 - 5.0 x ULN)	Maintain dose level

Recommended dose modifications for pasireotide LAR	
Worst toxicity CTCAE Grade* (value)	Recommended dose modification any time during a cycle of therapy
(>5.0 and ≤ 8 x ULN)	If ALT or AST return to less than 5 x ULN study drug can be resumed and patient can continue study per protocol. If persistent for more than 14 days, discontinue patient from study treatment. In the event of a re-occurrence, discontinue patient from study treatment.
(> 8 x ULN)	Omit dose and discontinue patient from study treatment
Pancreatic	
Pancreatitis	
Grade 1	Maintain dose level
Grade 2	Maintain dose level
Grade 3	Omit dose and discontinue patient from study treatment
Grade 4	Omit dose and discontinue patient from study treatment
Amylase and/or lipase	
Grade 1 (> ULN - 1.5 x ULN)	Maintain dose level
Grade 2 (> 1.5 - 2.0 x ULN)	Maintain dose level
Grade 3 (> 2.0 - 5.0 x ULN)	For asymptomatic: Omit dose until resolved to ≤ Grade 1, then - If resolved ≤ 7 days, then maintain dose level - If resolved > 7 days, then ↓ 1 dose level For symptomatic: Omit dose and discontinue patient from study treatment Omit dose and discontinue patient from study treatment A CT scan or other imaging study to assess the pancreas, liver and gallbladder must be performed within 1 week of the first occurrence of any ≥ CTCAE grade 3 of amylase and/or lipase.
Grade 4 (> 5.0 x ULN)	
Endocrine/metabolic	
Fasting plasma glucose (FPS) or 2-hour postprandial capillary glucose (PPG)	
FPG <126 mg/dL or PPG < 140 mg/dL	Maintain dose level
Grade 1 (> ULN – 160 mg/dL)	Please refer to Appendix 14.2 'Guideline for study drug-induced hyperglycemia'
Grade 2 (> 160 – 250 mg/dL)	
Grade 3 (> 250 – 500 mg/dL)	
Grade 5 (> 500 mg/dL)	
Cardiac	
Cardiac - prolonged QTc interval	
- QTcF > 480 ms and ≤ 500 ms	If at any time a QTcF > 480 ms and ≤ 500 ms is observed a cardiology consultation must be sought to re-evaluate the abnormal ECG finding.

Recommended dose modifications for pasireotide LAR	

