	Aspartate aminotransferase increased (PT)
	Blood cholinesterase abnormal (PT)
	Blood cholinesterase decreased (PT)
	Computerised tomogram liver abnormal (PT)
	Gamma-glutamyltransferase abnormal (PT)
	Gamma-glutamyltransferase increased (PT)
	Guanase increased (PT)
	Hepatic enzyme abnormal (PT)
	Hepatic enzyme decreased (PT)
	Hepatic enzyme increased (PT)
	Hepatic function abnormal (PT)
	Hepatobiliary scan abnormal (PT)

Category	Adverse Event Term
	Hyperammonaemia (PT)
	Hypertransaminasaemia (PT)
	Liver function test increased (PT)
	Transaminases abnormal (PT)
	Transaminases increased (PT)
	Ultrasound liver abnormal (PT)
	Urine bilirubin increased (PT)
AESI Low blood cell related AEs	Anaemia (PT)
	Febrile neutropenia (PT)
	Haematocrit decreased (PT)
	Haemoglobin decreased (PT)
	Leukopenia (PT)
	Lymphocyte count decreased (PT)
	Lymphopenia (PT)
	Neutropenia (PT)
	Platelet count decreased (PT)
	Red blood cell count decreased (PT)
	Thrombocytopenia (PT)
AESI Pancreatitis related AEs	Abdominal compartment syndrome (PT)
	Blood trypsin increased (PT)
	Fat necrosis (PT)
	Hyperlipasaemia (PT)
	Lipase abnormal (PT)
	Lipase increased (PT)
	Pancreatic enzyme abnormality (PT)
	Pancreatic enzymes abnormal (PT)
	Pancreatic enzymes increased (PT)
	Pancreatitis (PT)
	Pancreatitis acute (PT)
	Pancreatitis haemorrhagic (PT)
	Pancreatitis necrotising (PT)
	Pancreatitis relapsing (PT)
	Peripancreatic fluid collection (PT)
AESI QT-prolongation-related AEs	Cardiac arrest (PT)
	Cardiac death (PT)
	Cardiac fibrillation (PT)
	Cardio-respiratory arrest (PT)
	Electrocardiogram QT interval abnormal (PT)
	Electrocardiogram QT prolonged (PT)
	Electrocardiogram repolarisation abnormality (PT)

Category	Adverse Event Term
	Long QT syndrome (PT)
	Loss of consciousness (PT)
	Sudden cardiac death (PT)
	Sudden death (PT)
	Syncope (PT)
	Torsade de pointes (PT)
	Ventricular arrhythmia (PT)
	Ventricular fibrillation (PT)
	Ventricular flutter (PT)
	Ventricular tachyarrhythmia (PT)
	Ventricular tachycardia (PT)

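### The pancreatitis AESI list in SAP 8.2 has three lipase-specific terms but none for amylase, so the pancreatic AESI count can be understated

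*SAP*

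**What the plan says.** SAP 7.4.1 calls for a separate summary and listing of AESIs and refers to attachment 8.2 for the categories. It gives no rule for adding terms to them. SAP 7.1.1 and Protocol 10.5.3 name AESIs next to AEs and SAEs as a main basis of the safety assessment.

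In SAP 8.2 the pancreatitis group is alphabetical and opens with "Abdominal compartment syndrome (PT". It contains "Hyperlipasaemia (PT", "Lipase abnormal (PT" and "Lipase increased (PT" (PT marks a preferred term; these quotes stop before the closing bracket). It also has one trypsin term and three generic pancreatic-enzyme terms. No entry names amylase.

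The protocol handles the two enzymes together in three places:

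- Appendix 7, Table 14-6 (SOM230X2203): the pancreatic row, which opens "If amylase and/or lipase", sets repeat testing and imaging from grade 3.
- Appendix 10, Table 14-11 (SOM230D2101): a matching row for follow-up and imaging.
- Appendix 10, Table 14-12 (SOM230D2101): the row headed "Amylase and/or lipase" sets dose action by grade and symptoms.

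Protocol 8.1.2.1 makes a laboratory abnormality an AE if, among other reasons, it is clinically significant or requires a change in study treatment. Protocol 8.1.3 says that AESIs follow from ongoing safety review and are discussed in the Investigator Brochure.

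**The concern.** An AESI group is meant to collect all codings of one medical concept, so that its frequency does not depend on which term was chosen. Here the concept includes raised pancreatic enzymes, because lipase and trypsin each have their own terms. Amylase, which the protocol pairs with lipase, has none.

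Two patients can meet the same row of the protocol, one through lipase and one through amylase, and both can have a reportable AE. If each is coded to the enzyme-specific term, the first enters the pancreatic AESI table and the second does not. The error runs in one direction only. What is at stake is how complete the pancreatic AESI table is in a study whose main purpose is long-term safety.

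**Working it through.** There is no stated figure to reproduce. The check is a count of the list, a comparison with the protocol, and a trace of where an amylase-coded AE would be reported.

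**1. Count of the pancreatitis group in SAP 8.2**

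| Type of term | Number |
|---|---|
| Lipase-specific | 3 |
| Amylase-specific | 0 |
| Trypsin-specific | 1 |
| Generic pancreatic enzyme | 3 |
| Other (pancreatitis terms, fat necrosis, fluid collection, compartment syndrome) | 8 |
| Total | 3 + 0 + 1 + 3 + 8 = 15 |

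Reading the other AESI groups finds no amylase term there either.

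**2. Could a row have been lost when the PDF was read?** The 15 terms are in strict alphabetical order with no broken row. A term beginning with amylase would stand between the first entry and the trypsin term. By analogy with Hyperlipasaemia, a hyper- form would stand between Fat necrosis and Hyperlipasaemia. One lost row would not explain both absences.

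**3. Protocol against SAP**

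| Place in the protocol | Parent study | What amylase or lipase triggers | Parent study in SAP Tables 2-1 and 2-2? |
|---|---|---|---|
| Table 14-6 | SOM230X2203 | Repeat tests, imaging | Yes |
| Table 14-11 | SOM230D2101 | Repeat tests, imaging | No |
| Table 14-12 | SOM230D2101 | Dose action | No |

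Appendix 7 has no dosing rule specific to amylase. Its general rule for drug-related AEs of grade 3 or higher (Table 14-8) sets aside only liver-test increases, QT prolongation and hyperglycemia, so an amylase AE can fall under it. The AE definition in Protocol 8.1.2.1 applies to every patient, so amylase AEs are not confined to these two parent studies.

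**4. Where an amylase-coded AE is reported under SAP 7.4.1**

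- Treatment-emergent AE tables by system organ class and preferred term, and listings: yes.
- SAE, discontinuation, dose adjustment or interruption, and additional-therapy tables: yes, where the event qualifies.
- Pancreatic AESI table: no, unless the same patient also has an AE under one of the 15 listed terms.

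**5. Size.** Let n be the number of patients with at least one of the 15 terms, A the number with an amylase-specific AE, and m the number of those A patients with none of the 15 terms. The table reports n where n + m would be complete. The relative shortfall is m / (n + m), with 0 ≤ m ≤ A. The documents give none of n, A or m, so the shortfall cannot be computed.

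**The case against.** The strongest defence is that the AESI scope may be deliberate. Protocol 8.1.3 points to the Investigator Brochure, which is not available here, and a choice to follow lipase alone cannot be excluded. This stands, and it is why the fix allows a stated reason instead of an addition. Neither document gives such a reason, and the protocol's pairing of the enzymes points the other way.

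A second defence is that the three generic enzyme terms may catch amylase findings, and that Protocol 8.1.1 and 8.1.2.1 prefer a diagnosis to a laboratory term, which steers symptomatic cases to the listed pancreatitis terms. Both reduce m. Neither guarantees m = 0: the list gives lipase and trypsin their own entries beside the generic ones, and the preference for a diagnosis applies only where one is possible.

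A reader might also infer more than the documents support:

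- *Every patient with only an amylase event is missed.* Only those whose AE is coded to an amylase-specific term, with no listed term as well, are missed.
- *Such events appear nowhere but in the general AE table.* They also enter the SAE, discontinuation, dose-adjustment and additional-therapy outputs where they qualify.
- *The primary result is biased.* The endpoint in Protocol Table 3-1 and SAP Table 5-1 is the frequency and severity of AEs and SAEs, which does not depend on the AESI list. The analysis is descriptive.
- *Amylase drives dosing throughout the protocol.* The amylase-specific dosing rule is in Table 14-12 alone, for a parent study that the SAP's indication tables do not list.
- *The low-blood-cell group has the same gap.* It pairs a diagnosis with a count term for lymphocytes ("Lymphocyte count decreased (PT") and for platelets, and has no count term for neutrophils or white cells. But Neutropenia, Febrile neutropenia and Leukopenia are listed, Table 14-12 itself uses the diagnosis ("Neutropenia (ANC"), and it has no white-cell rule. This merits a consistency check, not a finding.

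**Conclusion.** The point holds in a limited form. As SAP 8.2 is written, an AE coded to an amylase-specific term is left out of the pancreatic AESI count, while the same event coded to lipase is included. The count can be understated but not overstated for this reason. The shortfall is m / (n + m); it is zero if every such patient also has a listed term, and its actual size is unknown.

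The conclusion rests on two assumptions: that the MedDRA version in use has amylase-specific preferred terms, and that the omission was not a deliberate decision recorded elsewhere. The consequence is confined to one supplementary safety grouping. It is worth correcting because the correction is nearly free before lock.

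**What to change.** Before database lock, do one of the following in SAP 8.2:

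- Add the amylase counterparts of the three listed lipase terms to the pancreatitis group, with names taken from the MedDRA version used for reporting; or
- State in one sentence why amylase is excluded.

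As an optional check at the same time, confirm whether count-decreased terms for neutrophils and white cells should accompany Neutropenia and Leukopenia, as is done for lymphocytes and platelets.

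The cost is a few lines of SAP text, the matching update of the AESI term list used in programming, and possibly a slightly higher AESI count. It needs no new data and no change to any clinical rule.
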